Post Excision/Mohs Fractional CO2 Resurfacing: A Quantitative and Qualitative Scar Analysis
Study
PI: [name]
NCT02130297
Document Date: 2/27/2019

	Protocol Title:	Post Excision/Mohs Fractional CO2 Resurfacing: A Quantitative and Qualitative Scar Analysis Study
	Principal Investigator Name/Contact Info:	[name] [contact]
	Primary Contact Name/Contact Info	[contact] (office) [contact]
	Date Revised:	2/27/2019
	Study Number:	IF# 2430986 HS# 14-00132 GCO# 14-0387

MSSM Protocol Template HRP-503a

Instructions:

1. Prepare a document with the following sections. Note that, depending on the nature of your research, certain sections below may not be applicable. Indicate N/A as appropriate, explaining where possible.
2. For any items described in the sponsor's protocol, grant application or other source documents submitted with the application, you may reference the title and page numbers of these documents rather than cutting and pasting into this document. **Do NOT refer to any derived documents, such as the Sample Consent document, or other internal documents required with the submission.**
3. If you reference page numbers, attach those pages to this protocol.
4. When you write a protocol, keep an electronic copy. You will need to modify this copy when making changes.

Brief Summary of Research (250-400 words):

The purpose of this study is to evaluate the benefits and the ideal timing of treating a surgical scar of the skin with an ablative fractionated CO2 laser. An attempt to quantify the amount of collagen that gets deposited during the healing process after being treated with the fractionated CO2 laser as compared to an untreated area of the scar will be performed through a split scar study. Subjects will be placed in one of three categories, based on the timing of when their scar will receive intervention after the excisional surgery. The clinical appearance of the scar will then be documented over several office visits and at week 16 of the scar having been treated with the CO2 laser, a biopsy will be taken of the treated half of the scar and also one from the untreated half. These samples will be evaluated by confocal microscopy and H+E staining to quantify the amount of collagen deposition as well as the architectural changes in both the treated and untreated areas of the surgical scar.

1) Objectives:

The purpose of this study is to evaluate the potential benefits of treating a surgical scar post excision with an ablative fractionated CO2 laser with the goal of decreasing the appearance and size of the scar. The hypothesis of the study is that the portion of the scar treated with laser will have an improved appearance and texture. An attempt will be made to quantify the difference in collagen deposition and architecture with the theory being that the treated portion of the scar will have an architectural change similar to normal “scar-less” tissue. A secondary objective of the study is to try and determine the ideal time to treat the surgical scar post-excision.

	Protocol Title:	Post Excision/Mohs Fractional CO2 Resurfacing: A Quantitative and Qualitative Scar Analysis Study
	Principal Investigator Name/Contact Info:	[name] [contact]
	Primary Contact Name/Contact Info	[contact] (office) [contact]
	Date Revised:	2/27/2019
	Study Number:	IF# 2430986 HS# 14-00132 GCO# 14-0387

2) Background

Improvement of scar appearance after surgery has been a concept that has been looked at for many years. Katz et al. showed in the early 90's through a split scar study that mechanicaFel dermabrasion improved the clinical appearance of excision scars of the skin when performed 8 weeks after the surgery. Recently, there has been a great interest in fractional ablative resurfacing to improve the appearance of scars that resulted from either trauma or burns. Previous studies have indicated that a noticeable clinical improvement can be achieved when treating these types of scars with a fractionated CO2 laser. Fractional photothermolysis produces a unique thermal damage pattern known as microthermal treatment zones. These zones can be characterized as multiple columns of thermal damage surrounded by areas of untreated tissue. It is this intervention pattern that has revolutionized the arena of ablative laser therapy and enabled laser platforms such as the erbium:YAG (2,940 nm) and the carbon dioxide (10,600) lasers to provide effective results with significantly less side effects and much shorter recovery time. A study published in the Feb. 2010 Archives of Dermatology by Weiss et al. looked at treating atrophic surgical and traumatic scars with ablative fractional resurfacing and found it to be a safe and effective intervention for improving the clinical appearance of scars. It is felt that the zones of ablation and coagulation that are created produce dermal remodeling, tissue tightening, new collagen formation and thus lead to a clinical improvement in atrophic scars. While the study by Weiss et al. attempted to quantify the subjective improvement of the treated scars with objective topographical skin imaging, there has not been an established methodology for quantitatively assessing dermal collagen architecture. This pilot study will attempt to quantify the difference in collagen architecture of the treated area of the surgical scar compared to the untreated area by using methodology involving confocal microscopy established by [name] et al. in the Feb. 2011 article in The American Journal of Pathology titled "A Quantitative Approach to Scar Analysis"

3) Setting of the Human Research

Subjects will attend their study visits in the outpatient offices at the [name], Department of Dermatology

4) Resources Available to Conduct the Human Research

Meeting the recruitment goals of this project will be feasible as the surgical division of Mount Sinai's Dermatology Department performs over 500 surgeries in a six month time period and the study is looking to recruit 45 patients, thus the study needs to recruit less than 10% of the patients having surgery.

At this time there will be 2 staff members involved in this research and each member has already participated in IRB approved protocols at Mount Sinai and currently work at the only

 Mount Sinai	Protocol Title:	Post Excision/Mohs Fractional CO2 Resurfacing: A Quantitative and Qualitative Scar Analysis Study
	Principal Investigator Name/Contact Info:	[name] [contact]
	Primary Contact Name/Contact Info	[contact] (office) [contact]
	Date Revised:	2/27/2019
	Study Number:	IF# 2430986 HS# 14-00132 GCO# 14-0387

study site involved in the research. All investigators have extensive experience operating the Lumenis Ultrapulse CO2 fractional laser. The pathology specimens will be reviewed by a board certified dermatopathologist with extensive experience in evaluating specimens with confocal microscopy. Any additional members that will be added to assist in the study will be required to review the initial protocol that was submitted to the IRB and any further revisions required by the IRB. The PI will ensure that all personnel that are added after initial IRB approval disclose any financial interests and complete their education requirements prior to beginning the study.

5) Study Design

a) Recruitment Methods

Study subjects will be recruited through referrals from dermatologists at Mount Sinai's Department of Dermatology Faculty Practice

b) Inclusion and Exclusion Criteria

Inclusion criteria

1. Must understand and voluntarily sign an informed consent form 2. Must be male or female and aged >18 years at the time of consent 3. Must be able to adhere to the study visit schedule and other protocol requirements 4. Patients undergoing skin excisions and Mohs surgery of the face/trunk/extremities

Exclusion criteria

1. Inability to provide voluntary informed consent 2. Use of laser or light based interventions to affected areas in past year 3. Fitzpatrick Skin types 3-5. 4. Surgical lesions located on the central chest 5. History of keloid formation 6. History of Accutane use in the last 6 months

c) Number of Subjects

We intend to recruit and enroll 45 patients for this pilot study

d) Study Timelines

The duration of an individual subject's participation in this study will be carried out over six months. Enrollment completion will be scheduled for April 2019.

e) Study Endpoints

	Protocol Title:	Post Excision/Mohs Fractional CO2 Resurfacing: A Quantitative and Qualitative Scar Analysis Study
	Principal Investigator Name/Contact Info:	[name] [contact]
	Primary Contact Name/Contact Info	[contact] (office) [contact]
	Date Revised:	2/27/2019
	Study Number:	IF# 2430986 HS# 14-00132 GCO# 14-0387

For primary end point refer to pg.17 , section 7.2.2.1 and for secondary end point refer to pg. 17, section 7.2.2.2

f) Procedures Involved in the Human Research

All patients participating in this investigator initiated split-scar study will receive ablative fractional resurfacing with the Deep and Active FX™ platforms of the Lumenis Ultrapulse CO2 laser. The settings for interventions of scars on the face with the Deep platform will be 15% coverage, 15mJ at 150 Hz and 15% coverage, 12.5 mJ at 150 Hz for off the face. The Active platform settings will be 90 mJ with a density of 3 for the face and 70 mJ and a density of 2 for off the face. The DeepFX™ platform will be applied to the scar prior to the ActiveFX™ platform. Half of the excision scar will be treated with the appropriate settings and half will go untreated. Subjects will be randomized to receive laser intervention at the time of the excision, ten days post-op or 8 weeks post-op. There will be a total of 15 subjects in each study group. Each study group will consist of 5 subjects with excisions on the face, 5 subjects with excisions on the trunk and 5 subjects with excisions on the extremities. General wound care for post surgical excision and laser therapy will include a topical antibiotic cream as well as a topical skin moisturizer and gauze dressing.

The screening visit will consist of reviewing inclusion/exclusion criteria and obtaining informed consent. There will be a total of 7 study visits to include the day of the excision, post-op day number 10 for suture removal as well as laser therapy if the subject has been randomized to that intervention group, 4 weeks post-op, 9 weeks post-op and laser intervention for subjects randomized to this time frame for intervention, 12 weeks post-op, 17 weeks post-op and 24 weeks post-op. Each visit will last approximately 30-45 minutes each in which clinical photos of the surgical scar will be taken and any wound care or side effects of the laser therapy or surgery will be addressed. Subjects will have a 3 mm punch biopsy taken from both the treated and untreated half of the scar at the post-op visit that correlates approximately with 8 weeks after having been treated with the laser (weeks 9 for two of the subject groups and week 17 for the final study group). These biopsy samples will be taken for the purpose of analyzing the ultrastructure of the collagen architecture. To evaluate this ultrastructure, confocal microscopy using fractional dimension and lacunarity analysis will be used. Further scar analysis will be performed by H&E staining photographs captured on an Olympus BX51 microscope (Olympus America Inc. Center Valley, PA) equipped with MicroFire 2.2 digital camera (Optronics, Goleta, CA) using PictureFrame 2.0 software at 40X magnification. Image analysis will then be performed using NIH's shareware program, ImageJ and the Scar index will be determined. Subjects will have the option of having the untreated portion of their scar treated at no charge at the end of the study if the subject is satisfied with the results of the study

 Mount Sinai	Protocol Title:	Post Excision/Mohs Fractional CO2 Resurfacing: A Quantitative and Qualitative Scar Analysis Study
	Principal Investigator Name/Contact Info:	[name] [contact]
	Primary Contact Name/Contact Info	[contact] (office) [contact]
	Date Revised:	2/27/2019
	Study Number:	IF# 2430986 HS# 14-00132 GCO# 14-0387

g) Specimen Banking

N/A

h) Data Management and Confidentiality

All records identifying the subject will be kept confidential and, to the extent permitted by the applicable laws and/or regulations, will not be made publicly available. Only the subject number will be recorded in the CRF, and if the subject name appears on any other document, it must be obliterated before a copy of the document is supplied to the sponsor. Study findings stored on a password protected computer will be encrypted and stored in accordance with local data protection laws. As part of the informed consent process, the subjects will be informed in writing that representatives of the IRB, or regulatory authorities may inspect their medical records to verify the information collected, and that all personal information made available for inspection will be handled in strictest confidence and in accordance with local data protection laws. If the results of the study are published, the subject's identity will remain confidential. Only the investigator will maintain a list to enable subjects to be identified. The biopsy specimens will be sent directly to the dermatopathology lab as per standard operating procedure of the department. The specimens will be analyzed then destroyed immediately as per hospital procedures for disposing biologic waste. Photographs will be taken of the scar. If the scar is present on the face, we will focus the picture in a manner that the subject's facial features are not identifiable to maintain their privacy. These photographs will be labeled with the patient ID number and the date. The pictures will not have any subject's name on them. They will be stored on a password protected computer until the study is over at which time they will be transferred onto a disc or USB drive and stored with the rest of the study documents. We will use the study photographs to study the effects of the laser on scars. The photographs will be used for documentation of the study and for the purpose of being viewed by the blinded third party to evaluate the scars and rate them. The camera will be stored in a locked filing cabinet in the PI's office which has a 24 hour keypad lock. All photos will be deleted from the camera after being loaded on to an encrypted and password protected desktop computer located in the PI's office. Only investigators and co-investigators will have access to the photo files

i) Provisions to Monitor the Data to Ensure the Safety of subjects

N/A

j) Withdrawal of Subjects

	Protocol Title:	Post Excision/Mohs Fractional CO2 Resurfacing: A Quantitative and Qualitative Scar Analysis Study
	Principal Investigator Name/Contact Info:	[name] [contact]
	Primary Contact Name/Contact Info	[contact] (office) [contact]
	Date Revised:	2/27/2019
	Study Number:	IF# 2430986 HS# 14-00132 GCO# 14-0387

If a patient develops an infection while on the study that is serious, he or she will be terminated from the study. If the infection is not serious, and is mild to moderate in severity, then the patient and the investigator will decide, based on whether the infection resolves and whether it is reasonably related to study drug, whether or not to keep the subject on the study. Severe infections will most likely result in termination from the study.

6) Risks to Subjects

The potential risks of this study include erythema post-laser intervention. Some patients may be at risk for potential pigmentation loss while hyperpigmentation can also be a risk; however, laser settings will be adjusted according to the particular area of the body being treated. In addition Fitzpatrick skin types III-V will be excluded from the study in order to minimize this risk. Common minor side effects may include crusting, mild swelling, redness or brown discoloration at the intervention site. In rare cases, hypertrophic scarring or infection may occur. The potential risks of having a biopsy include pain, local swelling, bleeding and/or infection. A small scar may result at the biopsy site. To minimize the appearance of scarring from the biopsy the size of the punch biopsy will be limited to 3 mm.

7) Provisions for Research Related Injury

In the event of related harm or injury the patient will be clinically evaluated by the treating physician. If harm is deemed to have occurred the patient will be triaged and treated in clinically standard treatment protocols. In the case of worsening scar then may consider other modalities (e.g. surgery with a z plasty, dermabrasion, intralesional kenalog, other lasers) or discoloration (other lasers to correct color or topical therapies).

8) Potential Benefits to Subjects

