6. As per the protocol, the energy setting for treating scars on the trunk and extremity will be reduced to minimize the risk of hyperpigmentation. In addition, subjects with Fitzpatrick skin types III-V will be excluded from the study to minimize the risk of a subject developing hyperpigmentation from the laser intervention.

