Post Excision/Mohs Fractional CO2 Resurfacing:
A Quantitative and Qualitative Scar Analysis Study

PI: [name]

NCT02130297

Document Date: 3/9/18

Post Excision/Mohs Fractional CO2 Resurfacing: A Quantitative and Qualitative Scar Analysis Study

PI: [name]

Date: 3/9/18

Statistical analyses

The scars were assessed 6 months after surgery. Each subject was asked if one scar half appeared cosmetically better than the other or if both halves looked cosmetically equivalent. A physician, blinded to treatment, then assessed each half of the scar according to the validated modified Manchester scar scale (MMSS).¹⁶

3mm punch biopsies were then extracted from each scar half and subjected to quantitative scar analysis. Biopsies were fixed in formalin then dehydrated, paraffin-embedded and breadloafed into sections for picrosirius red staining. For analysis of collagen architecture, confocal photographs were captured by a Leica[®] TCSSPMP confocal microscope (Leica Microsystems[®], Wetzlar, Germany) at 1000 fold magnification.¹⁷ Sections were scanned in 1 micron increments for the entire section thickness of 7 microns. Data of frame-mode images were recorded and stored as 512 pixel images. Fractal dimension (F_D) and lacunarity (L) analyses were performed on the confocal images using a previously described methodology.¹⁸

This method for quantitative scar analysis was chosen because confocal microscopy leverages the fluorescence properties of collagen and provides high resolution images of dermal structure. Scar tissue exhibits denser (higher F_D) and more homogenous (lower L) architecture compared with the looser, basket-weave pattern of normal skin. It, therefore, follows that cosmetically superior scar tissue should

closely resemble normal skin, with a lower F_D and higher L. Pairwise t-test comparison was performed using Stata[®] 12 software (StataCorp LLC, College Station, Texas).

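### Body site is a design stratum with its own laser settings, but the SAP names no site term or breakdown, so a pooled result would not show whether the effect holds on both face and off-face scars

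*Protocol*

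**What the plan says.** **Settings depend on site.** Protocol Section 5(f) gives the Deep platform settings as "15% coverage, 15mJ at 150 Hz and 15% coverage, 12.5 mJ at 150 Hz for off the face", the first set being for the face. For the second platform it says "The Active platform settings will be 90 mJ with a density of 3 for the face and 70 mJ and a density of 2 for" scars elsewhere. Item 6 of the list just before Section 10 confirms that this is deliberate: "the energy setting for treating scars on the trunk and extremity will be reduced to minimize the risk of hyperpigmentation".

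**Site is fixed by design.** Section 5(f) sets 15 subjects per timing group and adds: "Each study group will consist of 5 subjects with excisions on the face, 5 subjects with excisions on the trunk and 5 subjects" (these last 5 having extremity scars). Section 5(c) gives the total: "We intend to recruit and enroll 45 patients for this pilot study".

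**The comparison is within a scar.** Section 5(f): "Half of the excision scar will be treated with the appropriate settings and half will go untreated".

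**The analysis.** The inferential plan in the SAP is one sentence: "Pairwise t-test comparison was performed using Stata" (version 12). It names no site, setting or timing term and no breakdown by any of them. It does not say whether the test is run once on all subjects or separately by group.

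**The concern.** The protocol balances a factor that the analysis then neither uses nor reports. Face scars get one set of laser settings and trunk and extremity scars get another, so the effect of the laser could plausibly differ between them. If subjects are pooled, the reported effect is an average with one third of its weight on face scars and two thirds on off-face scars, and nothing in the SAP labels it that way.

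What is at stake is mainly interpretation. From a pooled mean, a reader cannot tell a uniform effect from one present only on the face or only off it. An effect confined to one site could be diluted towards no effect, or carried over to scars where it was absent. For a pilot, that breakdown is useful for planning a later trial. Some precision may also be lost, but only under a condition set out in the working.

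**Working it through.** **Inputs from the documents.** Three timing groups; 15 subjects per group; 5 face, 5 trunk and 5 extremity scars per group; total 45. Deep: 15 mJ face, 12.5 mJ off-face. Active: 90 mJ and density 3 face, 70 mJ and density 2 off-face.

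**Count.** 3 × 15 = 3 × 3 × 5 = 45, which agrees with Section 5(c). Face: 3 × 5 = 15. Off-face: 3 × 10 = 30. The supplied text gives no alpha, power, effect size or SD, so there is no power figure to reproduce.

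**Difference in settings.** Off-face energy is lower by 1 − 12.5/15 = 16.7% (Deep) and 1 − 70/90 = 22.2% (Active).

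**What a pooled mean estimates.** Pooled effect = (15 × face effect + 30 × off-face effect)/45.
- Effect E on face scars only: 15E/45 = 0.33E.
- Effect E on off-face scars only: 30E/45 = 0.67E.

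If the test is instead run within each timing group, the mix is 5 to 10, which gives the same weights.

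**When precision is lost.** Both halves of a scar share one body site, so any site difference in the level of scarring cancels in the treated-minus-untreated difference. Extra variance arises only if the laser effect itself differs between face and off-face scars. Let the SD of the paired difference within a site be 1 and the gap in effect be g SD.
- Pooled variance ≈ 1 + (1/3)(2/3)g² = 1 + 0.222g².
- g = 0.5: √1.056 = 1.027, so the pooled standard error is 2.7% larger.
- g = 1: √1.222 = 1.106, so it is 10.6% larger.

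With exactly 15 and 30 subjects, the expected sample variance is 1 + [15 × 30/(45 × 44)]g² = 1 + 0.227g², which gives 2.8% and 10.8%.

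**Power.** Assumptions: two-sided alpha 0.05, normal paired differences, and an average effect of 0.427 SD, which a paired t-test with n = 45 detects with 80% power when g = 0. Each row rests on 100,000 simulated trials, so a simulated power near 80% has a standard error of √(0.8 × 0.2/100,000), or about 0.13 percentage points.

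| Gap g (SD) | Pooled power | Site-stratified power |
|---|---|---|
| 0 | 80.3% | 80.2% |
| 0.5 | 78.4% | 80.0% |
| 1.0 | 73.5% | 80.0% |
| 1.5 | 64.9% | 79.9% |

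With no gap the two agree to within simulation error, so stratifying costs essentially nothing.

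**Validity of the pooled test.** With a zero average effect, its simulated type I error is 5.0% at g = 0, 4.4% at g = 0.5 and 3.0% at g = 1. It is conservative when the effect differs by site.

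**What the strata can show.** At 80% power and the same alpha, the detectable effect is about 0.78 SD for face scars (n = 15) and 0.53 SD for off-face scars (n = 30). A face versus off-face difference in effect would have to reach about 0.91 SD.

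**The case against.** The strongest reply is that the average over site-specific settings is the treatment policy under study. Protocol Section 1 asks about laser against no laser, and about timing; comparing settings or body sites is not an objective. The planned site mix is the same in every timing group, so if it is met, neither the treated-versus-untreated contrast nor a comparison of timing groups is biased by the settings. The documents give no evidence that the laser effect differs by site, and strata of 15 and 30 can resolve only large differences.

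Most of this stands, and it limits the point in three ways.
- A reader might infer that the pooled t-test is invalid, or always carries extra variance. Neither follows. Pairing removes site differences in scar level, and the simulated type I error does not exceed 5% beyond simulation error.
- A reader might infer that separate results would give an effect for each set of laser settings. They would not. Settings and face/off-face site coincide completely, so no analysis of these data can separate them.
- A reader might infer that the SAP prescribes one pooled test. It does not state the number or grouping of tests. Section 5(e) also refers to endpoint sections (7.2.2.1 and 7.2.2.2) that are not in the supplied text, so what they say about site cannot be checked.

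What the reply does not answer is that a coherent average still has to be labelled as one, and that a stratum built into the design is being left out of the analysis for no saving.

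**Conclusion.** The point holds as a gap in specification and reporting. It is not an error that invalidates the comparison. The SAP as supplied carries no site term or breakdown, although the protocol fixes site in every timing group and ties the laser settings to it. The consequence for interpretation is a 1:2 average that would show a site-confined effect at 0.33 or 0.67 of its size.

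The precision cost is conditional: none without a gap, about 1.6 power points (80.0 − 78.4) at a 0.5 SD gap, and 6.5 points (80.0 − 73.5) at 1 SD. These figures rest on the assumed alpha, a common within-site SD, an average effect of 0.427 SD and full recruitment at the planned mix. The size of any real gap is unknown. Because the remedy is nearly free, the change is worth making. The absence of any timing analysis, despite the secondary objective in Section 1, is the larger omission and can be repaired in the same model. Nothing here bears on which laser settings are right.

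**What to change.** Analyse the paired difference D (treated minus untreated half) for F_D, L and MMSS in a linear model with site and timing group. With a face indicator F, one form is D = μ + β(F − 1/3) + timing effects summing to zero + error. Then:
- μ is the overall effect at the planned mix;
- μ + (2/3)β is the face effect;
- μ − (1/3)β is the off-face effect;
- 45 − 4 = 41 residual degrees of freedom remain.

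Keep the 1/3 and 2/3 weights if recruitment departs from 5/5/5, so that the overall effect keeps its meaning. Face, trunk and extremity may be used as three levels instead.

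Report the overall estimate and the face and off-face estimates, each with a confidence interval, and label the site estimates exploratory. State that the overall effect averages over site-specific settings, and that settings and body site cannot be separated. State also how many tests are run and on which subjects.

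The cost is a few lines of SAP text and the added model terms, with no new subjects, visits or procedures. Site has to be in the dataset, which the 5/5/5 allocation implies but the supplied text does not show. The drawback is wide site-level intervals (n = 15 and 30), which should not be read as evidence of no effect at a site.

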Indicate specifically whether you will include or exclude each of the following populations:

Include	Exclude	Vulnerable Population Type
	X	Adults unable to consent
	X	Individuals who are not yet adults (e.g. infants, children, teenagers)
	X	Wards of the State (e.g. foster children)
	X	Pregnant women
	X	Prisoners

15) Multi-Site Human Research (Coordinating Center)

N/A

16) Community-Based Participatory Research

N/A

 Mount Sinai	Protocol Title:	Post Excision/Mohs Fractional CO2 Resurfacing: A Quantitative and Qualitative Scar Analysis Study
	Principal Investigator Name/Contact Info:	[name] [contact]
	Primary Contact Name/Contact Info	[contact] (office) [contact]
	Date Revised:	2/27/2019
	Study Number:	IF# 2430986 HS# 14-00132 GCO# 14-0387

17) Sharing of Results with Subjects

During participation in this study, subjects will not be able to access their research records. This will be done to prevent the knowledge of study results from affecting the reliability of the study. Subjects' information will be available should an emergency arise that would require their treating physician to know this information to best treat them. Subjects will have access to their research record and any study information that is part of that record when the study is over or earlier, if possible. The investigator is not required to release to subjects research information that is not part of their medical record. Subjects will always have access to their own clinical medical records while participating in this study.

18) IRB Review History

Approved through 4/15/2019. Seeking continuation for one year

19) Control of Drugs, Biologics, or Devices

Ablative fractional carbon dioxide laser is stored in a combination-locked room accessible only by clinical trials personnel

Note: The IDS has its own forms that must be completed and a review process that must be followed before the IDS representative will sign off on Appendix B for submission to the PPHS.

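### The free end-of-study laser session depends on satisfaction, and the apparently unmasked subject gives a preference before the blinded rating: a risk of bias that a change of sequence would reduce

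*Protocol*

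**What the plan says.** Protocol section 5 f) sets the design: "Half of the excision scar will be treated with the appropriate settings and half will go untreated". The same section gives subjects the "option of having the untreated portion of their scar treated at no charge at the end of the study if the subject is satisfied"; the sentence goes on to name the results of the study as the object of that satisfaction.

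The SAP (Statistical analyses) gives the time point, "The scars were assessed 6 months after surgery", and the order. First, "Each subject was asked if one scar half appeared cosmetically better than the other", with equivalence as the third possible answer. Next, "A physician, blinded to treatment, then assessed each half of the scar", using the modified Manchester scar scale.

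Protocol section 5 h) says that one use of the study photographs is "being viewed by the blinded third party to evaluate the scars and rate them". Protocol section 17 withholds research records from subjects during the study to "prevent the knowledge of study results from affecting the reliability of the study".

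**The concern.** The subject's preference is one of two cosmetic outcomes in the SAP. It is a matter of opinion, and nothing suggests that the person giving it is unaware of which half was lasered. The study also holds out a benefit at about the same time, on condition that the subject is satisfied. A subject who wants that benefit may shade the answer towards the laser.

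The order raises a second question. The physician rates after the subject has been asked. If both happen in the same room, the subject's opinion may reach the one clinical rater who is meant to be blinded. Agreement between the two outcomes could then be read as corroboration although they are not independent.

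**Working it through.** The plan contains no figure for this point, so most of the check sets the texts side by side.

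1. **Timing.** The last visit in section 5 f) is at 24 weeks, and 24/52 × 12 = 5.5 months. The SAP assessment is at 6 months, and section 5 d) puts participation at six months. The preference question and the end-of-study offer therefore fall at about the same time.

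2. **Masking.** The SAP blinds the physician only. The control half is left untreated and no sham is described. Section 6 lists visible reactions: "Common minor side effects may include crusting, mild swelling, redness or brown discoloration at the intervention site". That subjects know the treated half is a strong inference, not a statement in the text. Withholding records (section 17) does not hide it.

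3. **Link between offer and answer.** The condition is satisfaction with the study's results. The outcome is a three-way comparison of halves. The documents do not equate them, and do not say how or when satisfaction is established. Nor do they say that the preference answer is left out of that decision. It is the only subject-reported cosmetic rating described, so a subject could reasonably suppose that the two are connected.

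4. **Route to the physician.** The SAP states a sequence. It does not say whether the physician was present for the answer, could see it, or rated in person or from photographs. Section 5 h) has photographs labelled with patient ID and date for a blinded rater; the SAP mentions none in connection with the Manchester rating. Section 4 lists two staff members at one site, and section 5 h) limits the photograph files to investigators and co-investigators. Separation of the rater therefore needs to be written down.

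5. **Reach.** The offer gives the physician no incentive and has no route to fractal dimension or lacunarity. Section 5 e) defines the endpoints by reference to pages not in the supplied text, so the rank of preference cannot be determined.

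6. **Sensitivity of a preference outcome at this sample size (illustration only).** The sample is 3 timing groups × 15 = 45, with 15 = 3 body sites × 5; both reproduce. The SAP assigns no test to preference, so assume an exact two-sided sign test at 0.05, no equivalent answers and no true effect. Let a share b of those who would otherwise name the untreated half name the treated half, from any cause. Then p = 0.5 + 0.5b.

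The critical count r is the smallest with 2 × P(X ≥ r | n, 0.5) ≤ 0.05. That gives r = 30 for n = 45 (attained size 3.57%) and r = 12 for n = 15 (3.52%). The chance of a false finding for the laser is P(X ≥ r | n, p):

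| b | p | n = 45 | n = 15 |
|---|---|---|---|
| 0 | 0.50 | 1.8% | 1.8% |
| 0.1 | 0.55 | 7.6% | 4.2% |
| 0.2 | 0.60 | 22.5% | 9.1% |
| 0.3 | 0.65 | 47.5% | 17.3% |

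The documents give no value for b. The table shows that a modest tilt would matter, not that one exists.

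**The case against.** A reader might infer that answering equivalent, or preferring the untreated half, forfeits the offer, so that the study rewards one answer. The documents do not say this. A subject can be satisfied with the results and still see the halves as equal. The condition may only reflect that someone unhappy with the laser would not want more of it. The motive is also weak for many subjects: those who see matching halves have no unevenness to correct, those who prefer the untreated half have little reason to want it lasered, and those who truly prefer the lasered half need not distort anything. This stands, and it limits the point to a risk.

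A reader might also infer from the order that the blinded rating is contaminated. Order alone does not do that. The physician would have to hear or see the answer, and a rater working from the section 5 h) photographs need not meet the subject. Even if heard, a preference does not state which half was lasered. This stands too. What remains is that the text does not settle live or photographic rating, and does not say that the rater is kept from the subject's answer.

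Finally, the text of Protocol section 8 (potential benefits) and the consent pages was not available to me and may say more about the offer. The SAP is in the past tense, so some assessments may already be complete.

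**Conclusion.** The point holds as a risk of bias in the preference outcome, and as an unresolved question about how the blinded rating is protected. It rests on three things in the text: an offer conditional on satisfaction, a preference question at about the same time and before the physician's rating, and no described masking of the subject. It also rests on the inference that subjects know which half was lasered.

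The size of any bias cannot be estimated. Putting a number on it would require assuming how many subjects change their answer, and the result would only restate that assumption. The risk to the Manchester rating arises only if that rating is live, or if the rater otherwise has the subject's answer. The confocal measures are unaffected. This is a worthwhile, inexpensive improvement and not a flaw that undermines the trial.

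**What to change.** - **SAP, order and separation.** State whether the Manchester rating is made live or from the section 5 h) photographs. Either way, have the blinded physician complete it on halves coded A and B, before the subject is asked and without access to the subject's answer.
- **SAP, preference.** Record the subject's preference after that rating and before the offer is raised. Report it as an unmasked, supportive outcome.
- **Protocol section 5 f) and consent.** State that the recorded preference answer is not used to decide access to the offer. Whether further laser is given remains a matter for the investigator and subject.

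The cost is minor rewording, some attention to visit sequence and possibly a few more free sessions. The order can change only for subjects not yet assessed. For those already assessed, the report should say how the rating was made and whether the rater knew the subject's answer.
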